5.4. Safety Set

The Safety Set includes all randomized participants who receive any study intervention.

The Safety Set will be used for all analyses of safety data except for the solicited ARs. Participants will be included in the treatment group corresponding to the study intervention they actually received.

5.5. Solicited Safety Set

The Solicited Safety Set includes all randomized participants who receive any study intervention and contribute any solicited ARs data, i.e., have at least one post-baseline solicited safety assessment. The Solicited Safety Set will be used for the analyses of solicited ARs and participants will be included in the treatment group corresponding to the study intervention they actually received.

In addition, 2 subsets of the Solicited Safety Set are defined for Day 1 injection and Day 22 injection. Day 1 (Day 22) Solicited Safety Set consists of all participants in the Solicited Safety Set who have received the study injection on Day 1 (Day 22) and have contributed any solicited AR data from the time of study injection on Day 1 (Day 22) through the following 6 days.

6. Statistical Analysis

6.1. General Considerations

The Schedule of Activities is provided in Appendix F.

Continuous variables will be summarized using the following descriptive summary statistics: the number of participants (n), mean, standard deviation (SD), median, minimum (min), and maximum (max). For the summary statistics of all numerical variables, unless otherwise specified, the display precision will follow programming standards. Please see Appendix A for variable display standards.

Categorical variables will be summarized using counts and percentages. When count data are presented, the percentage will be suppressed when the count is zero to draw attention to the non-zero counts. A row denoted "Missing" will be included in count tabulations where specified on the shells to account for dropouts and missing values. The denominator for all percentages will be the number of participants in that treatment group within the analysis set of interest, unless otherwise specified.

Baseline value is defined as the most recent non-missing measurement (scheduled or unscheduled) collected before the Day 1 injection, unless otherwise specified. For immunogenicity assessments, the baseline is defined as the following:

- Influenza Abs for all participants randomized to Study Arm 1 or Arm 2: The baseline is defined as the most recent non-missing result/measurement (scheduled or unscheduled) collected before or on the date of the Day 1 injection.
- RSV Abs for participants randomized to Study Arm 1: The baseline is defined as the most recent non-missing result/measurement (scheduled or unscheduled) collected before or on the date of the Day 1 injection.
- RSV Abs for participants randomized to Study Arm 2: The baseline is defined as the
 most recent non-missing result/measurement (scheduled or unscheduled) collected before
 or on the date of the Day 22 injection.

Study day relative to the Day 1 injection will be calculated as below:

a) Study day prior to the Day 1 injection will be calculated as: date of assessment/event – date of the Day 1 injection (resulting in negative study day).

b) Study day on or after the date of the Day 1 injection will be calculated as: date of assessment/event – date of the Day 1 injection + 1.

Study day relative to the most recent injection will be calculated as below:

- a) Study day prior to the Day 1 injection will be calculated as: date of assessment/event date of the Day 1 injection;
- b) Study day on or after the date of the Day 1 injection but before the Day 22 injection (if applicable) will be calculated as: date of assessment/event date of the Day 1 injection + 1;
- c) Study day on or after the date of the Day 22 injection will be calculated as: date of assessment/event date of the Day 22 injection + 1; if study day is on the same day as the Day 22 injection, date and time will be compared with the Day 22 injection date and time. If it is prior to the Day 22 injection, then study day is calculated as bullet point b); if it is after the Day 22 injection or the time is missing or not available then study day is calculated as: date of assessment/event date of the Day 22 injection + 1.

For GMT and GMC calculation, antibody values reported as below the LLOQ will be replaced by $0.5 \times \text{LLOQ}$ and antibody values greater than the ULOQ will be converted to the ULOQ.

Unscheduled visits: Unscheduled visit measurements will be included in analysis as follows:

- In the derivation of baseline measurements.
- In scheduled visit windows per specified visit windowing rules.
- In individual participant data listings as appropriate.

Visit windowing rules: The analysis visit windows for protocol-defined visits are provided in Appendix B.

Incomplete/missing data:

- Imputation rules for missing dates of prior/concomitant medications and non-study vaccinations are provided in Appendix C.
- Imputation rules for missing dates of prior/concomitant procedures are provided in Appendix D.
- Imputation rules for missing AE dates are provided in Appendix E.
- Other incomplete/missing data will not be imputed, unless specified otherwise.

Treatment groups:

The following treatment groups will be used for summary purposes:

- D1: Fluzone HD+mRNA-1345 (μg) and D22: placebo
- D1: Fluzone HD+placebo and D22: mRNA-1345 (μg)

If a subject receives any dose of mRNA-1345 on Day 1, regardless of the treatment group the subject is randomized to, the subject will be included in the actual treatment group "D1: Fluzone HD+mRNA-1345 (µg) and D22: placebo" for safety and reactogenicity analyses.

All analyses and data summaries/displays for disposition, demographics and baseline characteristics, safety and immunogenicity will be provided by treatment group using appropriate analysis population, unless otherwise specified. Local solicited adverse reactions will be also summarized by injection content (mRNA-1345, Placebo and Fluzone HD).

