For the immunogenicity endpoints, the GMT/GMC ratio of specific Abs, with the corresponding 95% CI at each timepoint, and geometric mean fold rise (GMFR) of specific Ab titers, with the corresponding 95% CI at each postbaseline timepoint over preinjection baseline, will be provided by treatment group. The 95% CIs will be calculated based on the t-distribution of the log-transformed values then back-transformed to the original scale. Descriptive summary statistics, including the median, minimum, and maximum values, will also be provided.

For summarizations of the GMT/GMC ratios, Ab titers reported as below the LLOQ will be replaced by 0.5×LLOQ. Values that are greater than the ULOQ will be converted to the ULOQ if actual values are not available.

The proportion of participants with at least 2-fold and SRR titers/concentration (relative to baseline) will be provided by timepoint with the 2-sided 95% CI using the Clopper-Pearson method as well.

Descriptive statistics (including 95% CIs) of the immunogenicity endpoints will also be provided by treatment group and age group (65 to 74 years, and ≥75 years).

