SOC	System organ class
SMQ	Standardized MedDRA Queries
SRR	Seroresponse rate
TFLs	Tables, Figures, and Listings
ULOQ	Upper limit of quantification
WHO-DD	World Health Organization Drug Dictionary

1. Introduction

This statistical analysis plan (SAP), version 1.0, is based on the approved clinical study protocol (CSP) (original version, dated 21-Jul-2023) and the approved eCRF (version 1.0, dated on 20-Sep-2023).

In addition to the information presented in the statistical consideration sections of the protocol (Section 9) which provides the principal features of analyses for this study, this SAP provides statistical analysis details/data derivations. It also documents modifications or additions to the analysis plan which are not "principal" in nature and result from information that was not available at the time of protocol finalization. If the methods in this SAP differ from the methods described in the protocol, the SAP will prevail.

Study mRNA-1345-P304 is a Phase 3, randomized, observer-blind study to evaluate safety, tolerability, and immunogenicity of mRNA-1345, an mRNA vaccine targeting respiratory syncytial virus (RSV), when coadministered with a high-dose (HD), quadrivalent seasonal influenza vaccine in adults ≥65 years of age.

PPD Biostatistics and programming team, designee of Moderna Biostatistics and Programming department, will perform the statistical analysis. Statistical Analysis System (SAS) Version 9.4 or higher will be used.

In this document, intervention, injection and dose are used interchangeably.

2. Study Objectives

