6.4.2.1. Primary Analysis Approach

The coprimary endpoints include the following:

- GMT of serum RSV-A and RSV-B nAbs at Day 22 (Arm 1) and Day 43 (Arm 2)
- GMT of serum influenza anti-HA Abs as measured by HAI assay at Day 22

The statistical analyses are:

• For each coprimary endpoint, the GMR will be estimated using an analysis of covariance (ANVOVA) model on the log-transformed titers, with the treatment group and log-transformed baseline titers as the fixed covariate, adjusted for stratified age group used for randomization. The geometric least square mean (GLSM) for each treatment group and its corresponding 95% CI in a log-transformed scale will be estimated from the model and back-transformed to obtain these estimates in the original scale as an estimate of the GMT and its 95% CI. The GMR estimated by the ratio of the GLSMs and the corresponding 2-sided 95% CI will be provided to assess the treatment difference in the immune response between the 2 treatment groups. For each coprimary endpoint, the

noninferiority of the GMT will be demonstrated if the LB of the 95% CI of the GMR is >0.667 based on a noninferiority margin of 1.5.

• Additionally, GMT of RSV-A nAb, RSV-B nAb, and influenza anti-HA Abs for each influenza strain with corresponding 95% CI will be provided at each visit (as applicable) by treatment group. The 95% CIs will be calculated based on the t-distribution of the log-transformed values and then back transformed to the original scale for presentation. The following descriptive statistics will also be provided at each visit: the number of participants (n), median, minimum and maximum. GMT with 95% CI will be plotted at each visit (as applicable) by treatment group.

The study is considered to meet the primary immunogenicity objective if the noninferiority of the immune response to mRNA-1345 coadministered with Fluzone HD is met based on all the coprimary endpoints.

The above analysis corresponds to the Primary Immune Estimands 1a-2a as described in Appendix G, Table 5.

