6.4.2.2. Sensitivity Analysis

Analyses of the primary endpoints will be performed based on the FAS, using the same method and same definition as described in Section 6.4.2.1.

This sensitivity analysis corresponds to the Supportive Immune Estimands 1b-2b as described in Appendix G, Table 5.

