6.5. Multiplicity Adjustment

A sequential/hierarchical testing procedure will be used to control the overall Type 1 error rate at 0.05 (2-sided) over the primary endpoints, and secondary endpoints.

The coprimary endpoints will be tested at the planned primary analysis at a 2-sided Type 1 error rate of 0.05. The success criteria of all 6 coprimary endpoints need to be met in order to declare the study a success to achieve noninferiority of coadministration.

The secondary endpoints on SRR and SCR will only be tested at the primary analysis at a 2-sided Type 1 error rate of 0.05 when all coprimary endpoints have achieved statistical significance. The secondary endpoints will be tested sequentially in the following order: 1) SCR of influenza anti-HA Abs for each influenza strain, 2) SRR of RSV-A nAbs and 3) SRR of RSV-B nAbs.

No further testing will be performed once the sequence/hierarch breaks, that is, further testing stops as soon as an endpoint in the sequence fails to meet success criterion of noninferiority. Analyses of remaining other secondary immune endpoints are not controlled for multiplicity.

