6.6. Planned Analyses

The following analyses will be conducted on cleaned data:

1. The primary analysis of safety and immunogenicity data will be performed after all participants have completed Day 43 visit. All data relevant to the primary study analysis through the Day 43 Visit will be cleaned and locked for the primary analysis (i.e., data that are as clean as possible) and a report may be generated. The primary analysis will be performed by a separate team of unblinded programmers and statisticians.

2. The final analysis of all endpoints will be performed after all participants have completed Day 202/EoS. Results of this analysis will be presented in a final CSR.

7. Changes from Planned Analyses in Protocol

The following changes from planned analyses in the study protocol are included in this document:

• Appendix G Estimands and Estimand Specification: Estimands language has been added for primary immune endpoint and primary safety endpoint.

8. References

U.S. Department of Health and Human Services, Food and Drug Administration, Center for Biologics Evaluation and Research. Guidance for industry: Toxicity grading scale for healthy adult and adolescent volunteers enrolled in preventive vaccine clinical trials. September 2007[cited 2022 Jan 11]. Available from: https://www.fda.gov/media/73679/download.

9. List of Appendices

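### The SAP caps every titer above the ULOQ, dropping the protocol's condition that capping applies only where no actual value exists; the change is undeclared and can pull the coprimary GMRs toward 1

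*SAP*

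**What the plan says.** Protocol Section 9.5.1 sets two substitution rules for the GMT/GMC ratio summaries. The lower-limit rule reads "For summarizations of the GMT/GMC ratios, Ab titers reported as below the LLOQ will be replaced by 0.5×LLOQ". The upper-limit rule is conditional: "Values that are greater than the ULOQ will be converted to the ULOQ if actual values are not available".

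SAP Section 6.1 (General Considerations) repeats the lower-limit rule unchanged for GMT and GMC calculation. It gives the upper-limit rule without the condition: "antibody values greater than the ULOQ will be converted to the ULOQ".

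Four other places determine what this means in practice:

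- SAP Section 1 (Introduction): "If the methods in this SAP differ from the methods described in the protocol, the SAP will prevail".
- SAP Section 7 (Changes from Planned Analyses in Protocol) has one entry: "Estimands language has been added for primary immune endpoint and primary safety endpoint".
- SAP Section 6.4.2.1 estimates each coprimary GMR by ANCOVA on log titers, "with the treatment group and log-transformed baseline titers as the fixed covariate", adjusted for the age stratum. Noninferiority requires a lower 95% confidence bound above 0.667.
- SAP Section 6.4.2.2, the only sensitivity analysis of the coprimary endpoints, moves to the FAS "using the same method and same definition as described in Section 6.4.2.1".

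**The concern.** Where the laboratory reports a number above the ULOQ, the protocol keeps it and the SAP discards it. The SAP governs, so the unconditional cap would be programmed although no document records a decision to change the rule. Protocol Section 9 says that changes to the methods for primary or secondary hypotheses, made after the study starts and before unblinding, lead to a protocol amendment.

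Direction matters in a noninferiority trial. If the two arms have similarly shaped titer distributions and coadministration lowers the response, a common cap trims the higher (reference) arm more. The GMR moves toward 1 and the SD falls, and both raise the lower confidence bound. The FAS analysis cannot show this because it uses the same method. SAP Section 6.1 also does not say whether the rule applies to the ANCOVA's outcome and baseline titers.

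**Working it through.** **Inputs from the documents** (SAP Sections 4.3 and 6.4.2.1; Protocol Section 9.3): 855 evaluable per arm, SD 1.5 on the natural-log scale, planning GMR 0.9, margin 1.5 (lower bound above 0.667), two-sided alpha 0.05.

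**Inputs that must be assumed**, because the documents give no ULOQ, no share of titers above it and no statement on whether values beyond it are reported: log-normal titers; p, the share of the reference arm above the ULOQ; q, the fraction of those values that have an actual number.

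**Step 1: the plan's own power.** Standard error = 1.5 × √(2/855) = 0.0725. Power = Φ[(ln 0.9 − ln 0.667)/0.0725 − 1.96] = Φ(4.13 − 1.96) = 98.5%, and 0.985⁶ = 91.3%. Both match the plan.

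**Step 2: effect of the cap.** Take the reference mean as 0, the test mean as μ = ln(GMR) and the cap as c = 1.5 × z(1−p). With a = (c − μ)/1.5, the capped titer has

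- E[min(X,c)] = μΦ(a) − 1.5φ(a) + c[1 − Φ(a)]
- E[min(X,c)²] = (μ² + 1.5²)Φ(a) − 1.5(μ + c)φ(a) + c²[1 − Φ(a)]

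With d the difference in capped means and v₁, v₀ the capped variances, P(declare NI) = Φ[(d + ln 1.5)/√((v₁ + v₀)/855) − 1.96].

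**Step 3: one case in full** (true GMR 2/3, p = 10%). c = 1.922. Capped means are −0.4445 (test) and −0.0710 (reference), so d = −0.3735 and the apparent GMR is e^(−0.3735) = 0.688. Capped variances are 2.022 and 1.883, against 2.25 uncapped, so the standard error is √(3.905/855) = 0.0676. Then (−0.3735 + 0.4055)/0.0676 = 0.473, and Φ(0.473 − 1.96) = 6.9%. Without the cap it is Φ(−1.96) = 2.5%.

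**Step 4: across shares, true GMR at the margin, per endpoint**

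| Reference arm above ULOQ | Apparent GMR, SAP rule | False NI, SAP rule | False NI, protocol rule, all actual values available |
|---|---|---|---|
| 1% | 0.669 | 2.7% | 2.5% |
| 2% | 0.671 | 3.0% | 2.5% |
| 5% | 0.677 | 4.1% | 2.5% |
| 10% | 0.688 | 6.9% | 2.5% |
| 20% | 0.713 | 18.7% | 2.5% |

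If only half the values above the ULOQ have a number (q = 0.5, mixing capped and uncapped moments equally), the protocol rule gives 3.2% at 5% and 4.2% at 10%, against 4.1% and 6.9% under the SAP rule. If none do (q = 0), the two rules are identical.

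**Step 5: away from the margin, SAP rule**

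- True GMR 0.9: power moves from 98.5% to 99.2% (5% share) or 99.6% (10% share).
- True GMR 0.6: the pass rate is at most 0.9% for shares up to 20%.
- True GMR 1.1: the pull is downward, to 1.089 at a 10% share.

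**Step 6: the planned model.** A simulated ANCOVA with baseline and age stratum (10,000 trials per setting, outcome capped, baseline uncapped, assumed baseline correlation 0.3, 0.5 or 0.7) gives false noninferiority of 4.2%, 4.2% or 4.7% at a 5% share and 7.3%, 8.1% or 9.5% at 10%. A separate simulation with baseline also capped, correlation 0.5 and 3,000 trials gives 5.0% and 7.6%.

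**The case against.** The strongest reply is that the documents do not show any effect on the results. An effect needs actual numbers above the ULOQ, a material share of titers there and a true GMR near 0.667. If the laboratory reports nothing beyond the ULOQ, the SAP may only have dropped redundant words. This stands: the range starts at zero, and the 18.7% figure is an extreme case, not an expectation.

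Two further points also stand in part. One calculation is used for two RSV neutralization endpoints and four HAI endpoints, whose upper limits may differ. SAP Section 6.5 adds that "The success criteria of all 6 coprimary endpoints need to be met in order to declare the study a success", so capping in one assay cannot by itself produce study success. Each rate above is therefore an upper limit on false study success within its own scenario only; other SDs or baseline correlations give other rates.

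It can also be argued that the back-transformed model means are GMT estimates, so the SAP rule already reaches the ANCOVA outcome. That is the natural reading, and it strengthens the link to the coprimary endpoints. The baseline covariate remains unstated.

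Finally, capping is a defensible convention, since such values lie outside the quantifiable range. That would be a reason to give for the change. It does not excuse leaving it undeclared when the protocol chose the opposite.

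**Conclusion.** The concern holds. The condition was dropped, the SAP version governs, Section 7 does not declare it, and no planned analysis would reveal its effect. These facts do not depend on any assumption.

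The numerical impact is conditional: nil if no actual values above the ULOQ exist, negligible at a 1% share, and, for a true GMR at the margin with all actual values available, about 4% to 5% false noninferiority per endpoint at a 5% share and 7% to 10% at a 10% share, against 2.5%. These figures rest on log-normal titers, SD 1.5, 855 per arm and equal spread in both arms. At the planned GMR of 0.9 the change is slight, and the plan's sample size is unaffected. This should be corrected, but it is not a fatal defect.

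**What to change.** Before unblinding:

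1. Restore the protocol's condition in SAP Section 6.1: use the reported value where there is one and substitute the ULOQ only otherwise.
2. State that the rule applies to both the outcome and the baseline titers in the ANCOVA.
3. Report the number of values above the ULOQ by arm, assay and visit.

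If unconditional capping is intended, list it in SAP Section 7 with a reason, check it against the amendment commitment in Protocol Section 9, and add a sensitivity analysis of the coprimary endpoints on actual values. A censored-normal (Tobit) ANCOVA is optional and worth considering only if a material share remains capped.

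The cost of restoring the condition is one SAP sentence and one count table, with no repeat assays. Doing it now avoids having to choose between two conflicting written rules once results are known.

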4.2. Scientific Rationale for Study Design

In this study, only participants ≥65 years of age were considered due to the preferentially recommended influenza Fluzone HD Quadrivalent vaccine and the Sponsor's position that the coadministration of mRNA-1345 with a seasonal influenza vaccine will allow people to receive both vaccines at once to reduce the number of visits and add to the uptake/convenience in people at risk for both RSV and influenza diseases, further described in Section 2. Justification for Dose

Participants will receive 1 dose of mRNA-1345 µg administered on either Day 1 or Day 22 (refer to Table 3). The µg dose was chosen based on the observed reactogenicity and immunogenicity profiles in clinical Phase 1, 2, and 3 studies conducted with mRNA-1345.

Selected dose level for the Phase 2/3 study in adults ≥60 years: Based on the Study mRNA-1345-P101 Phase 1 data in adults aged 65 to 79 years, a single μg injection was selected to be evaluated in the mRNA-1345-P301 Phase 2/3 pivotal efficacy and safety study, based on an optimal combination of an acceptable safety profile and boosting and persistence of RSV nAb titers. At the μg dose level, the reported rate of any local or systemic solicited AR was 72.3%, with injection site pain the most commonly reported (65.9%). Most of the participants reporting any solicited AR at this dose level experienced mild, Grade 1 severity (59.6%), with lower rates of moderate, Grade 2 severity (6.4%) observed. In comparison, the reported rate of any local or systemic solicited AR in the placebo group was 45.5%.

mRNA-1345

Results from a prespecified interim analysis of the ongoing pivotal efficacy and safety study in adults ≥60 years of age, mRNA-1345-P301 (Section 2.2), demonstrate that the primary efficacy objectives were met, including:

- Vaccine efficacy of 83.7% (95.88% CI: 66.0, 92.2) against RSV-LRTD, defined by ≥2 symptoms and 82.4% (96.36% CI: 34.8, 95.3), defined by ≥3 symptoms.
- mRNA-1345 was generally well tolerated, with no safety concerns identified.

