All analyses of solicited ARs will be provided separately after Day 1 injection and Day 22injection by treatment group as defined in Section 6.1 based on the Day 1 (Day 22) Solicited Safety Set. Summaries of local solicited ARs will be also presented by treatment group and injection content (mRAN-1345, Fluzone HD, and Placebo).

The number and percentage of participants with any solicited ARs, any solicited local ARs and any solicited systemic ARs during the 7-day follow-up period after each injection will be summarized by treatment group with a 2-sided 95% exact CI using the Clopper-Pearson method. Refer to Safety Estimand 3a in Appendix G, Table 6.

The following summaries for solicited ARs will be presented by treatment group:

- The number and percentage of participants who reported any solicited ARs, any solicited local ARs and any solicited systemic ARs within 30 minutes after each injection.
- The number and percentage of participants who reported each individual solicited AR (has a severity grade of Grade 1 or greater) during the 7-day follow-up period after each injection will be summarized by severity grade. For each local solicited AR after Day 1 injection, the summary will be based on the highest grade of the ARs observed from both injection sites (left and right arm).
- The number and percentage of participants who reported each individual solicited AR will be summarized by the onset day relative to the corresponding injection (Day 1 through Day 7). The onset day of an individual solicited AR is defined as the time point after each injection at which the respective solicited AR first occurred. For each local solicited AR after Day 1 injection, the summary will be based on the earliest onset day of the ARs from both injection sites (left and right arm).
- The duration (days) of each individual solicited AR will be summarized descriptively for each injection. The duration will be calculated as: end date of solicited AR event reaction start date of solicited AR event +1, no matter if it is intermittent or continued or if the solicited AR continues beyond 7 days. For each local solicited AR after Day 1

injection, the summary will be based on the longest duration of the ARs observed from both injection sites (left and right arm).

• The number and percentage of participants who reported each individual solicited AR that continue beyond 7 days post-injection will be summarized for each injection.

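### SAP 6.1 sets the actual treatment group from Day 1 dosing alone, so some Day 22 systemic reactions and unsolicited AEs after mRNA-1345 would be tabulated under a placebo label

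*SAP*

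**What the plan says.** SAP 6.1 introduces the summary groups with "The following treatment groups will be used for summary purposes" and lists two: the coadministration regimen (mRNA-1345 on Day 1, placebo on Day 22) and the sequential regimen (placebo on Day 1, mRNA-1345 on Day 22), each with Fluzone HD on Day 1. One actual-treatment rule follows: "If a subject receives any dose of mRNA-1345 on Day 1, regardless of the treatment group the subject is randomized to", the participant goes into the coadministration group "for safety and reactogenicity analyses". There is no group for mRNA-1345 at both visits.

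The analysis-set definitions state a general principle. SAP 5.4 (Safety Set): "Participants will be included in the treatment group corresponding to the study intervention they actually received". SAP 5.5 (Solicited Safety Set): "participants will be included in the treatment group corresponding to the study intervention they actually received".

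The tables are built by visit. SAP 6.3.1 says "All analyses of solicited ARs will be provided separately after Day 1 injection and Day 22injection by treatment group as defined in" Section 6.1. SAP 6.3.2 likewise summarises unsolicited AEs to 21 days separately after each injection. For local reactions there is an extra layer: "Summaries of local solicited ARs will be also presented by treatment group and injection content". Protocol 4.2, under the dose justification, plans one dose of mRNA-1345 per participant, "administered on either Day 1 or Day 22".

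**The concern.** The phrase about randomized group shows that the rule was written with dosing errors in mind, yet it looks at only one of the two visits. A participant with mRNA-1345 on both days is carried into the Day 22 tables under a label that says placebo. Systemic reactions, unsolicited AEs and any SAE or AESI in the 21 days after that injection are then counted as if they followed saline.

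Safety and reactogenicity form a primary objective. The coadministration arm after Day 22 is the only place in the study where the visit's injection is saline alone, because both arms receive Fluzone HD on Day 1. A reader of the Day 22 tables will take that column at face value. Two-dose exposure also lies outside the planned regimen, so a safety reader would want it identified where the events are tabulated.

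**Working it through.** No stated figure in the plan is at issue. The check is a trace through the rules, followed by a sizing calculation.

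**Trace.** Each dosing pattern is passed through SAP 6.1:

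| Randomized arm | mRNA-1345 on Day 1 | Day 22 product | Group under SAP 6.1 | Day 22 label correct? |
|---|---|---|---|---|
| Arm 1, as planned | Yes | Placebo | Coadministration | Yes |
| Arm 2, as planned | No | mRNA-1345 | Sequential | Yes |
| Arm 2, regimens swapped | Yes (error) | Placebo (error) | Coadministration | Yes |
| Arm 2, Day 1 error only | Yes (error) | mRNA-1345 | Coadministration | **No** |
| Arm 1, Day 22 error only | Yes | mRNA-1345 (error) | Coadministration | **No** |

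The rule works when the whole regimen is swapped. It fails in the last two rows.

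**Do these participants reach the Day 22 tables?** Yes. The Day 22 Solicited Safety Set (SAP 5.5) requires a Day 22 injection and diary data, whatever the content. A wrong intervention leads to exclusion from the PP Set (SAP 6.2.7) but not from the Safety Set. In SAP Appendix G it is part of IcEv3, and Table 6 handles IcEv1 to IcEv4 by treatment policy.

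**What separates them out?** Injection content is tabulated for local solicited reactions only, and within treatment group. Systemic reactions and unsolicited AEs have no such split. SAP 6.2.6 lists participants with a dosing error but does not re-tabulate them.

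**Size.** Inputs: about 950 per group (SAP 4.3); rate of any local or systemic solicited reaction 72.3% after mRNA-1345 and 45.5% after placebo (Phase 1, Protocol 4.2). The number of two-dose participants, k, is an assumption. The denominator is held at 950.

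- Ceiling, where each participant has the event and would not have had it after placebo: k/950. For k = 1, 1/950 = 0.105%, or 0.11 points. For k = 5 and 10 (about 0.5% and 1% of 950), 0.53 and 1.05 points.
- Expected shift from the Phase 1 rates: k × (0.723 − 0.455)/950 = k × 0.268/950.

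| k (assumed) | Ceiling (points) | Expected (points) |
|---|---|---|
| 1 | 0.11 | 0.03 |
| 5 | 0.53 | 0.14 |
| 10 | 1.05 | 0.28 |
| 19 (2%) | 2.00 | 0.54 |

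The Day 22 denominator will be somewhat below 950. With 855 (the SAP's PP figure, borrowed only as a lower value), the values for one participant are 1/855 = 0.12 and 0.268/855 = 0.03 points. The Phase 1 rates pool local and systemic reactions to a single injection, so they only indicate the order of magnitude for systemic reactions after a second dose.

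**The case against.** The strongest reply is that the SAP foresees wrong dosing and deals with it deliberately. Appendix G names it as an intercurrent event and counts all safety events under treatment policy. Only two regimen groups exist, a two-dose participant matches neither, and some convention is needed. The safety estimands compare whole regimens, with the sequential arm as reference. Within that comparison, the rule charges double-dose events to the coadministration arm, which does not flatter it. This stands as a defence of keeping these participants in the regimen groups. It does not defend a Day 22 table whose column label misstates the Day 22 product.

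Three stronger readings are tempting, and the documents do not support them.

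- *The rule distorts a planned placebo comparison.* No Day 22 contrast of placebo with mRNA-1345 and no safety hypothesis test is planned; the safety summaries are descriptive.
- *The rule conceals repeat dosing, or would be decisive for a rare AESI.* Dosing errors are listed (SAP 6.2.6), important deviations are tabulated by group (SAP 6.2.7), AESIs and SAEs have individual listings (SAP 6.3.2.1), and suspected myocarditis and pericarditis go to a blinded adjudication committee (SAP 6.3.2.7). One AESI could sit under the wrong Day 22 label, but it would be traceable. In the throughout-study tables both columns contain mRNA-1345, so there is no placebo period to contaminate.
- *Participants with two doses or no dose of mRNA-1345 should be excluded from the regimen columns.* The SAP has no explicit rule for those with no dose, and neither label fits them. But they include Arm 2 participants who stop before Day 22, a category that SAP 6.2.1 tabulates. Arm 1 participants who stop equally early have already had mRNA-1345 and would remain. The exclusion would be post-randomization and unequal by arm, and would conflict with the Safety Set definition and the treatment-policy estimand.

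**Conclusion.** The point holds as a narrow labelling defect. For a participant given mRNA-1345 at both visits, SAP 6.1 places Day 22 systemic reactions and 21-day unsolicited AEs under a placebo label, which SAP 5.4 and 5.5 would not lead a reader to expect. It arises only through a dosing error. The documents give no error rate, assignment is central (Protocol 6.3), and dosing is observed and reconciled with accountability records (Protocol 6.5).

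The size is at most 0.11 points per participant and about 0.03 expected, given a denominator near 950 and the Phase 1 rates. Five to ten such participants, an assumed number, would move the any-reaction percentage by about 0.14 to 0.28 points. The coprimary conclusions are unaffected, because the immunogenicity analysis uses the PP Set as randomized and wrong-intervention participants are excluded from it. This is a worthwhile clarification and does not threaten the trial's conclusions.

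**What to change.** Amend SAP 6.1 as follows:

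- For solicited reactions after the Day 22 injection, and unsolicited AEs in the 21 days after it, group participants by the product actually injected on Day 22.
- Keep the present rule for Day 1 summaries.
- Footnote or list participants who received mRNA-1345 at both visits, so that second-dose events are not read as first-dose experience in the Day 22 mRNA-1345 column.
- Keep every participant in the throughout-study Safety Set tables under the treatment-policy estimand. Do not exclude those with two doses or no dose of mRNA-1345.

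The cost is a few lines of text and one derivation from injection-level content, which the local-reaction tables already need. Column denominators may differ slightly between Day 1 and Day 22 tables, and a footnote can explain this.
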